Study Protocol and Statistical Analysis Plan

Speech Locator In-car Performance Evaluation— ID# SRF-459

Jan 27, 2022

NCT05054816

Speech Locator In-car Performance Evaluation—ID# SRF-459

1 Objectives and hypotheses of the clinical investigation

1.1 Purpose of the clinical investigation claims for clinical performance, effectiveness or safety of the investigational device that are to be verified

The insight on general and individual preferences between the investigational feature and comparator features will be used to determine if and when the investigational feature should be included in an upcoming platform release. The initial clinical evaluation of the development of this feature has been requested by Research & Development.

1.2 Primary and Secondary Objectives

The primary objective of this study is to measure the subjective impression of the investigational feature (using overall impression and listening effort ratings) in 20 experienced hearing aid users with mild to severe hearing loss.

The second objective is to determine if there are any audible artifacts while implementing the feature, and if there are, measure how bothersome they are to the listener.

2 Design of the clinical investigation

2.1 General

2.1.1 Design Type

This is a randomized, double-blinded in-person study with participants serving as self-controls.

2.1.2 Measures for minimizing bias

Bias will be minimized by (1) randomizing stimuli presentation and (2) double-blinding of stimuli through automated playback.

2.1.3 Endpoints with rationale for their selection and measurement

Ratings are expected to be different among different test conditions. An internal evaluation has been completed with normal hearing employees, who reported audible differences for all selected sound dimensions. Rationales for the specific rating dimensions are as the following:

Speech clarity ratings: Participants will be instructed to "Please rate the clarity of speech". Speech clarity ratings will be measured on a 100-point continuous slider from worst to best (0-Very unclear, 25-Unclear, 50-Slightly clear, 75-Clear, 100-Very clear). Speech clarity ratings are expected to be impacted by how intelligible the speech is. Participants will rate and compare speech clarity between the investigational and comparator features.

Noise annoyance ratings: Participants will be instructed to "Please rate how annoying the noise is". Noise annoyance ratings will be measured on a 100-point continuous slider from worst to best (0-Extremely annoying, 25-Very annoying, 50-Moderately annoying, 75-Slightly annoying, 100-Not at all annoying). Noise annoyance ratings are expected to be impacted by how bothersome the background

noise in the recordings is. Participants will rate and compare noise annoyance between the investigational and comparator features.

Spatialization ratings: Participants will be instructed to "Please rate your confidence that the talker is in [a location]", with the local being either passenger of rear left. Spatialization ratings will be measured on a 100-point continuous slider from worst to best (0-I don't know where the talker is, 25-The talker might be to my [location], 50-The talker is probably to my [location], 75-The talker is to my [location], 100-The talker is definitely to my [location]). Spatialization ratings are expected to be impacted by how well the recordings preserve spatial perception. Participants will rate and compare spatialization between the investigational and comparator features.

Overall impression ratings: Participants will be instructed to "All things considered, please rate overall preferences". Overall preferences ratings will be measured on a 100-point continuous slider from worst to best (0-Bad, 25-Poor, 50-Fair, 75-Good, 100-Excellent). Overall impression ratings are expected to be impacted by participants' overall preferences for the different stimuli. Participants will rate and compare overall impression between the investigational and comparator features.

Transition annoyance ratings: Participants will be instructed to "Please rate how annoying the transitions are". Transitions annoyance ratings will be measured on a 100-point continuous slider from worst to best (0-Extremely annoying, 25-Very annoying, 50-Moderately annoying, 75-Slightly annoying, 100-Not at all annoying). Transition annoyance ratings are expected to be influenced by presence of unexpected sounds or transitions that occur in different microphone modes and different listening situations. Participants will rate and compare transition annoyance between the investigational and comparator features.

2.2 Procedures

2.2.1 Investigation-related Procedure

Participant eligibility is determined based on case history on file. The case history consists of audiograms, etiology of hearing loss, other medical information, and personal details like age, gender, contact information, occupation, hobbies, etc. Case history information is gathered prior to the study and as a part of database management, which is a separate process from this investigation.

Participants will be screened for the study using an outreach email and/or call. After successful completion of screening, participants will sign the consent form and complete the demographic questionnaire upon arrival for their first session.

2.2.2 Sponsor activities

Study sponsor is responsible for participant recruitment, assessment, data collection, analysis and monitoring.

2.2.3 Outcome comprising factors

Participants need to meet the hearing loss criteria in order to judge the differences in the recordings for the targeted hearing loss group. If participants cannot tolerate the loudness of the output, they could miss these differences. Therefore, we will recruit only experienced hearing aid wearers.

Participants need to be tech-savvy to the extent that they are comfortable operating the subjective HPP tool using a touchscreen interface, keyboard and/or mice. We will ask for their ability to do so during the screening call. If problems arise during the study session and support cannot solve the issue, the participant will be withdrawn from the study.

Subjective ratings often are not as sensitive as objective outcome measures because participants need to pay attention to small differences. The sound samples have been selected with regards to representation of scenes in which the hearing aid processing produces audible differences. Questions will be formulated in a way that draws participants' attention to the anticipated area of focus (i.e. speech, talker location, microphone mode)

3 Statistical design and analysis

3.1 Determination of Sample Size

We will recruit up to 25 participants, including up to 5 pilot participants. Previous research with subjective ratings has repeatedly shown that data collected with 15-25 participants can yield significant results.

3.2 Statistical criteria of termination of trial

If the results are significant after 15 participants have completing the protocol, we will consider terminating the data collection.

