3.3 Planned Analyses

The statistical analysis plan includes the methods and types of the analysis, the variables the data sets and the timeframe when the (interim) analysis is planned. Recall that participants will be completing three repetitions of each stimulus. Repetitions will be averaged within each participant prior to analysis. Reliability within each participant will also be assessed to determine if that participant's data should be included the analysis.

- Repeated-measures analysis of variance (RM-ANOVA) to detect significant effects
- Post-hoc pairwise comparisons to locate the source of significant effects

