3.3.1 Datasets to be analyzed, analysis population

Analysis population: 15-25 participants

Evaluation group: rating per setting

Data sets: subjective ratings

- Additional analyses:
 - Individual preferences and their potential dependences, such as hearing loss,

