3.3.2 Primary Analysis

The study manager will analyze the collected data set in R Statistics after the data collection is completed. Microsoft Excel and MATLAB may be used for arranging data and plotting data sets.

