3.3.4 Interim Analysis

The study manager will analyze the collected data set in R Statistics in real time as the data collection is completed. Microsoft Excel and MATLAB may be used for arranging data and plotting data sets.

4 Informed consent process

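### Section 3.2 allows stopping on unadjusted significance at 15 participants; at an assumed 5% level, two looks raise the false-positive rate per rating to as much as 7.5–8.1%

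*Combined protocol and SAP*

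**What the plan says.** The stopping rule is one sentence in section 3.2: "If the results are significant after 15 participants have completing the protocol, we will consider terminating the data collection". Five other places bear on it.

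- **Timing.** Section 3.3.4 (Interim Analysis): "The study manager will analyze the collected data set in R Statistics in real time as the data collection is completed". Section 3.3.2 (Primary Analysis): "The study manager will analyze the collected data set in R Statistics after the data collection is completed". Section 3.3.3 says the same for the secondary analysis. No number of looks is given.
- **Tests.** Section 3.3 plans a repeated-measures ANOVA followed by pairwise comparisons. It states no level and no adjustment.
- **Ratings.** Section 1.2 names overall impression and listening effort as the primary measures. Section 2.1.3 defines five ratings (speech clarity, noise annoyance, spatialization, overall impression, transition annoyance). Listening effort is not among them.
- **Who is analysed.** Section 3.3: "Reliability within each participant will also be assessed to determine if" a participant's data are kept.
- **Final number.** Section 1.2 says "in 20 experienced hearing aid users with mild to severe hearing loss". Section 3.1 says "We will recruit up to 25 participants, including up to 5 pilot participants". Section 3.3.1 says "Analysis population: 15-25 participants".

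**The concern.** A significance test at 15 that can end the study, followed if it does not by a second test that includes the same 15 people, is a two-look sequential design. If each look uses the full nominal level, the chance of at least one false positive exceeds that level. The reported p-value then understates how easily chance could have produced the result. Stopping on a favourable fluctuation also pushes the average estimate away from zero.

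The rule also cannot be applied the same way by two people. It does not say which rating or which test must be significant. It counts participants who finished the protocol, although some may later be dropped for unreliability, and it does not say whether pilot participants count towards the 15. Each gap leaves a choice that could be made after the data are seen.

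Section 1.1 says the results will be used to decide whether and when the feature enters a platform release. A false positive, or an inflated preference, would feed directly into that decision.

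**Working it through.** The plan states no alpha, power, effect size or SD, so there is no figure of its own to reproduce.

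**Inputs from the document.** First look at 15 (section 3.2). Final number 20 (section 1.2; also 25 − 5 = 20 if all five pilots are excluded) or 25 (section 3.1, pilots included).

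**Assumptions not in the document.** Two-sided 5% at each look; a significant look always ends the study; 2 to 6 conditions for the ANOVA, with sphericity.

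**1. Two looks, normal approximation.** With no true effect, the test statistics at 15 and at N are correlated ρ = √(15/N). The false-positive rate is 1 − P(|Z₁| ≤ 1.96 and |Z₂| ≤ 1.96).

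- N = 20: ρ = √0.75 = 0.866, rate 7.3%.
- N = 25: ρ = √0.60 = 0.775, rate 8.0%.

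**2. Two looks, small-sample tests (simulation).**

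| Test | One look at 20 | Looks at 15 and 20 | Looks at 15 and 25 |
|---|---|---|---|
| Paired t (2 conditions) | 5.0% | 7.5% | 8.1% |
| RM-ANOVA omnibus (3–6 conditions) | nominal 5% | 7.5–7.6% | 8.1–8.3% |

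**3. Allowing for discretion.** If a significant look at 15 ends the study half the time, the rate is the average of the one-look and two-look rates: (5.0 + 7.5)/2 ≈ 6.2% and (5.0 + 8.1)/2 ≈ 6.5%.

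**4. If section 3.3.4 means a test after every participant from 15.** For a paired contrast the rate is 9.3% (to 20) or 11.9% (to 25). This is the extreme reading.

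**5. If any of the five ratings can trigger the stop.** The correlations between ratings are assumed. Paired tests at 5% each:

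| Correlation | One look at 20 | Looks at 15 and 20 | Added by the second look |
|---|---|---|---|
| 0.3 | 20.9% | 29.7% | 8.8 points |
| 0.5 | 18.6% | 26.4% | 7.8 points |
| 0.8 | 13.3% | 19.1% | 5.8 points |

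Only the last column belongs to section 3.2. The one-look column is multiplicity across ratings, a separate matter.

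**6. Bias.** Bias is (mean reported estimate − true effect)/true effect, over all trials, with full 5% looks. At true effects of 0.3–0.5 SD it is about 5% for looks at 15 and 20, and about 8% for 15 and 25. At 0.66 SD it falls to 3.3% and 5.3%. In absolute terms, 5% of 0.4 SD is 0.02 SD, against a standard error of 1/√20 = 0.22 SD at 20 participants.

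**7. Adjusted thresholds.** Testing at p<0.019 (15) then p<0.042 (20) gives an overall rate of 4.9–5.0%. Testing at p<0.010 (15) then p<0.046 (25) gives 5.0–5.1%. Both hold for the paired contrast and for an ANOVA with 3–4 conditions.

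**The case against.** The strongest reply has four parts.

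- **The rule is permissive.** It commits the sponsor only to consider stopping, so the full inflation need not occur. This stands as a limit on size: 7.5–8.1% is an upper range for two looks, and 6.2–6.5% is the half-the-time case. It does not remove the problem, because a discretionary rule leaves the error rate undefined and still lets a significant look be acted on.
- **The timing passages need not conflict.** Sections 3.3.2 and 3.3.3 concern the final analyses and section 3.3.4 the interim one, and section 3.2 names a single count of 15. One look is the more natural reading, so the headline rests on two looks in total. The wording of section 3.3.4 nevertheless leaves the number of looks open.
- **Multiplicity, the missing listening-effort rating, pilots and reliability exclusions are separate defects.** Agreed. They matter here only because each leaves the stopping rule's trigger or its count of 15 undefined. The defect from section 3.2 alone is about 2.5 to 3 points per rating.
- **This is an initial evaluation requested by Research & Development.** The documents tie no regulatory or safety claim to the result. That limits the seriousness. But the plan itself makes significance the stopping criterion and uses the result for a release decision, so the error rate attached to that criterion should be known. The bias is also small beside the sampling error.

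**Conclusion.** The concern holds. Followed as written, section 3.2 inflates the false-positive rate; it is more than a missing detail. At an assumed two-sided 5% per look, with a significant look always ending the study, the rate per rating goes from 5.0% to 7.5% (15 and 20) or 8.1% (15 and 25), and the ANOVA results lie within 0.2 points of these. Discretion in applying the rule lowers the figures; more looks, or several ratings able to trigger the stop, raise them. The average overestimate is modest: roughly 5% or 8% at true effects of 0.3–0.5 SD, and less at larger effects. The inflation does not invalidate the study, but it should be corrected because the remedy costs little. That the plan gives no level, threshold or named rating does not depend on any assumption.

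**What to change.** **Preferred.** Replace section 3.2 with:

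> Data collection will not be stopped for statistical significance. Inferential tests are run once, after the planned number of participants is complete.

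State that number (section 1.2 gives 20) and whether pilot participants are part of it. Replace section 3.3.4 with:

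> No interim inferential analysis is planned. Checks during collection are limited to completeness and data quality.

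The cost is at most 20 − 15 = 5 further listeners, or 25 − 15 = 10, all within the recruitment already planned.

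**If an early stop is kept.** State alpha, and name one primary rating and one test. Allow a single look, at 15 participants who remain analysable after the reliability check, and say whether pilots count. Use adjusted thresholds, for example p<0.019 at 15 and p<0.042 at a final 20, or p<0.010 at 15 and p<0.046 at a final 25. The second pair can exceed 5% by less than 0.1 point; lower its final threshold slightly if strict control is wanted.

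Power cost against one final test at 5%, paired contrast:

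| True effect | Final 20: one test → adjusted | Final 25: one test → adjusted |
|---|---|---|
| 0.4 SD | 39.7% → 38.2% | 48.4% → 47.7% |
| 0.5 SD | 56.5% → 54.6% | 67.0% → 66.1% |
| 0.66 SD | 80.0% → 78.4% | 88.6% → 88.1% |

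The loss is under 2 points at 20 and under 1 point at 25. Either option needs only protocol and SAP wording. Neither deals with multiplicity across the five ratings, which needs its own rule.

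### Stopping at 15 because the result is significant makes the difference reported after an early stop too large on average, and a stricter threshold alone does not cure this

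*Combined protocol and SAP*

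**What the plan says.** Section 1.2 frames the main aim as estimation: "The primary objective of this study is to measure the subjective impression of the investigational feature", and names the group as "in 20 experienced hearing aid users with mild to severe hearing loss". Section 1.1 says the insight on preferences "will be used to determine if and when the investigational feature should be included in an upcoming platform release".

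Section 3.2 sets the stopping rule: "If the results are significant after 15 participants have completing the protocol, we will consider terminating the data collection". It names no rating, no contrast and no significance level. Section 3.3.4 provides for an interim analysis in real time and fixes no number of looks.

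On numbers, section 3.1 says "We will recruit up to 25 participants, including up to 5 pilot participants", and section 3.3.1 gives "Analysis population: 15-25 participants". The planned methods in section 3.3 are "Repeated-measures analysis of variance (RM-ANOVA) to detect significant effects" and post-hoc pairwise comparisons. Nothing in sections 3.3 to 3.3.4 gives an adjusted estimate or interval, or says how a difference would be reported after an early stop.

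**The concern.** A significance trigger selects on the quantity the study sets out to measure. With 15 listeners, only a fairly large observed difference reaches significance. Studies that stop there are therefore disproportionately those in which chance pushed the difference away from zero. Studies that continue are those in which it did not, and their estimates run low.

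This is a problem of estimation, separate from the false-positive rate. Choosing a stricter interim threshold repairs the error rate, but it raises the bar the observed difference must clear and so increases the average excess among studies that stop. A sponsor who only added an alpha boundary would leave the estimate uncorrected. At stake is the size of the rating difference presented when the feature is considered for release.

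**Working it through.** **The plan's own figure.** The sample size cannot be reproduced. Section 3.1 supports it only with the statement "Previous research with subjective ratings has repeatedly shown that data collected with 15-25 participants can yield significant results". There is no alpha, power, SD or effect size.

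**Inputs.**
- From the documents: look at 15 (section 3.2), final size 20 (section 1.2), within-participant comparison (section 2.1.1), three repetitions averaged per participant (section 3.3).
- Assumed: two-sided 5%; one paired contrast standing in for the RM-ANOVA and its pairwise follow-up; normal differences with SD 1; a binding rule with a single look; true differences of 0.25 to 1.0 SD.

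**Step 1: what a stop requires.** A paired t-test is significant when |mean difference| / observed SD > t(0.975; n−1)/√n. At n = 15 this is 2.145/√15 = 0.554 observed SDs.

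**Step 2: mean estimate given a stop.** Simulation: stop at 15 if significant, otherwise estimate at 20. The last column is a trial with fixed n = 20 and no interim look, counting only significant results.

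| True difference (SD) | Stops at 15 | Mean estimate given a stop | Excess | Fixed 20, significant only |
|---|---|---|---|---|
| 0.4 | 30% | 0.68 | +69% | 0.61 (+51%) |
| 0.5 | 44% | 0.72 | +43% | 0.65 (+29%) |
| 0.65 | 65% | 0.79 | +21% | 0.73 (+12%) |
| 0.8 | 82% | 0.88 | +10% | 0.83 (+4%) |
| 1.0 | 95% | 1.03 | +3% | 1.01 (+1%) |

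Percentages are from unrounded means, for example 0.676/0.4 = 1.69 and 0.647/0.5 = 1.29.

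**Step 3: stricter thresholds.** With an interim threshold of p < 0.015, the excess rises to +90%, +59% and +32% at true differences of 0.4, 0.5 and 0.65 SD. With boundaries solved to hold overall alpha at 5% and a final size of 20, the mean early-stop estimate at a true 0.5 SD is 0.74 (Pocock-type) or 0.78 (O'Brien-Fleming-type), against 0.72 unadjusted.

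**Step 4: all trials together.** Studies that continue underestimate: at a true 0.4 SD they average 0.31. Combining, 0.30 × 0.676 + 0.70 × 0.31 = 0.42, or +5%. Across the effects examined, the overall bias is about 6% or less with a final size of 20. With a final size of 25 it reaches about 8% at 0.2 to 0.5 SD.

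**Step 5: the ordinary 95% interval after an early stop.** Coverage is 82% at a true 0.25 SD (where about 15% of trials stop), 92% at 0.4, 94% at 0.5 and 96% at 0.65. Over all trials it is about 95%.

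**Step 6: a trigger that ignores the size of the difference.** Suppose the study stops at 15 when the 95% half-width is at most 0.54 SD, which about half of trials meet. The mean early-stop estimate is then 0.40 for a true 0.4 and 0.65 for a true 0.65. Overall coverage is 94.6% and the false-positive rate 5.4%. Coverage given a stop is about 92%, because the rule favours samples with a low observed SD.

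**The case against.** The best case for the plan has four parts.

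- **Much of the excess is not special to this rule.** Any significant result from a small study is inflated on average, as the last column of the table shows. This stands, and the early-stop figures should not be quoted without that comparator. It does not remove the point: a fixed trial of 20 reports one unbiased estimate whatever the p-value, whereas here the p-value decides when the estimate is taken.
- **The overall bias is small.** At a true 0.5 SD it is about 0.02 SD, against a standard error of 1/√20 = 0.22 SD. This also stands. But the sponsor will hold one study, and if it stopped at 15 the relevant figure is the one given a stop.
- **The effect may be large.** Sections 2.1.3 and 2.2.3 refer to audible differences and to sound samples chosen to show them. At 0.8 to 1.0 SD the excess is only 10% to 3%. Section 2.2.3 also says listeners must attend to small differences, so neither end of the range can be excluded.
- **The rule is discretionary, and no effect-size threshold for release is given.** Discretion lowers how often a stop occurs but does not undo the selection when one does. The absence of a release threshold limits the consequence, although section 1.2 still makes measurement the primary objective.

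A reader might infer that every early-stopped study must overstate the difference. That is not so: the 0.554 cut-off is in observed-SD units, and about 8% of early stops at a true 0.5 SD, and 25% at 0.65, fall below the truth. Nor is the ordinary interval generally unreliable; the shortfall is confined to small effects.

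**Conclusion.** The point holds as a statement about averages. Under section 3.2 as written, the difference reported after a stop at 15 is too large on average, nothing in section 3.3 corrects it, and a stricter threshold alone makes the early-stop excess larger. The size runs from about +69% at a true 0.4 SD to about +3% at 1.0 SD, part of which is ordinary selection on significance.

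The documents do not support the stronger reading that the study as a whole would be badly biased, or that the stopping rule causes the full excess.

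All magnitudes rest on the assumed 5% level, a single look, one contrast and standardised effects that the documents do not state. If significance is judged on one of several ratings, the excess will concentrate in whichever comparison triggered the stop. The weakness is real and cheap to remove.

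**What to change.** In section 3.2, remove significance as the trigger and adopt one of two rules:

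1. Run to the 20 participants named in section 1.2.
2. After 15 analysable participants, stop only if the 95% confidence-interval half-width for the overall-impression difference (investigational minus comparator) is at or below a number of slider points fixed before the main data are seen; otherwise continue to 20. The documents give no SD from which to set that number, but the pilot participants' data could inform it.

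If a significance trigger is kept, define it on one named contrast, state in the report that the study stopped early, and add to section 3.3 a conditional (selection-adjusted) estimate and interval beside the ordinary ones. A median-unbiased estimate under the usual stage-wise ordering would not help: for a stop at the first look it equals the ordinary estimate.

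The cost is a sentence or two in section 3.2 and a few lines of R. Some studies that would have stopped at 15 will run to 20, which is within planned enrolment. The precision rule also gives up some power relative to the significance trigger, and its interval covers about 92% given an early stop.
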